Due to the pathogenesis of neuromuscular deformity patients with such conditions have inevitable progression of spine and thorax deformity, even patients with the mature skeleton and minimal deviations (up to 20-25° by Cobb) in frontal and/or sagittal plane (Larsson E.L. et al., 2005). Early usage of rigid corset prevents significant progression at the childhood but can cause contact dermatitis and pressure ulcers. In this connection many authors insist on surgical spine stabilization at the second growth spurt (Master D.L., 2011). Patients with such conditions usually have severe and long C-type and S-type deformities with pelvic misalignment in frontal and sagittal planes. With S-type deformity body balance is often compensated, but both curves can reach 100° or more (Lonstein J., 2001). With deformity over 40° patients lose the ability to get to the vertical position and can sit only with the support. With deformity over 90° patients cannot sit (Bridwell K.H. et al., 1999; Berven S., Bradford D., 2002; Wang C.H. et al., 2007; Auerbach J.D. et al.m 2009; [name] et al., 2013). Patients in a wheelchair (III functional class by GMFCS - Gross Motor Function Classification System) have high risks of severe deformities in comparison with the bed-bound patients, due to the constant axial load (Lonstein J., 2001; Teli M. et al., 2005). Frequent reference to cardiopulmonary failure as main diagnosis in autopsy results confirms that decompensated spine deformity is the main reason for premature death of such patients (Pehrsson K., 1992; Berven S., 2002; Larsson E.L. et al., 2005; Sarwark J., 2007; Chong H.S., 2011).

Duchenne muscular dystrophy patients studies showed disease progression in all patients with deformity over 40° associated with difficulties while sitting, decrease in vital capacity, decreased performance and problems with hand movements (Hsu, 1983).

Indications for surgical correction of scoliosis in patients with NMD are progressive deformity, loss of balance while seating, back pain and discomfort (Herring JA., 2002; Labelle H, 2002; Renshaw TS, 2001). Such surgery can be performed using connector systems («growing rods») (McElroy MJ, 2011; Chandran S, 2011). The main outcome of treating scoliosis is the stabilization of respiratory parameters and increase in patient activity level (Daher YH, 1985; Brown JC, 1988; Rodillo E, 1989; Phillips DP, 1989; Bridwell KH, 1999; Larsson EL, 2005).

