1.3. Study description

This study was sponsored by Federal state budgetary institution “Russian scientific center for traumatology and orthopedics” n.a. acad. G.A. Ilizarov” of the Ministry of Health of Russian Federation. The study will take place at this center.

[figure not shown]
It is expected to enroll 70 patients aged 10-18 years with NMD, all of whom will be subjected to thoracic and lumbar spinal deformity surgery.

Patients will be divided into two groups depending on skeletal maturity. The degree of skeletal maturity will be determined on the basis of an X-ray study of spinal and pelvic bones. The type of surgical correction will depend on the group.

[figure not shown]

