3. STUDY PLAN

3.1. Study goals and objectives

1. To estimate effectiveness and safety of surgical treatment for spinal deformities with different pedicle screw fixation (PSF) systems in various pediatric patient groups with neuromuscular diseases
2. Considering patient condition, deformity progression, age, physical, motor, cognitive, functional, static and dynamic status present the following:
 - a) Develop diagnostic algorithm for patients with severe deformities of thoracic and lumbar spine following NMD
 - b) Create surgery planning algorithm: instrumentation area planning, number and location of fixation points planning, grounds for spine mobilization and area of mobilization
 - c) Assess effectiveness of the intraoperative safety control technologies - navigation and monitoring during surgical treatment of spinal deformities in NMD patients (Nim Eclipse, Stealth Station S7)
 - d) Evaluate dynamics in physical, static, dynamic and functional status after surgical treatment using special scales

We assume that the study will result in the following:

- introduction of modern surgical methods of treating children with severe spinal deformities at NMD;

CHILDren with neuromuscular diseases – efficacy eVALuation of spinal deformity surgeRY via different pedicle screw fixation systems study
 CHIVALRY study

- development and simulation of individual methods of surgery and spinal system elements for treating children with severe spinal deformities at NMD.

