3.3. Study design

This study is prospective, non-randomized, single-center, open and non-comparative; it involves two parallel groups of patients (children aged 10-18 years) with severe thoracic and lumbar spinal deformities at NMD.

Patients are divided into groups depending on skeletal maturity determined on the basis of an X-ray study of spinal and pelvic bones. The type of surgical correction will depend on the group.

1. Group of patients with spinal deformities corrected and stabilized with bilateral connector systems (growing skeleton).

Bone maturity grades I-III (Sadofyeva classification) or I-II (Risser classification).

Bilateral connector systems (“growing rods”) will be used in this group (N = 30).

2. Group of patients with spinal deformities corrected and stabilized with bilateral multiple fixation points (mature skeleton).

Bone maturity grades IV-V (Sadofyeva classification) or III-IV (Risser classification).

Inside this group (N=40) two subgroups are planned depending on varying anatomic characteristics thus allowing for specific treatment option:

- *Subgroup 1 – segmental fixation*
- *Subgroup 2 – intermittent (next nearest) segment fixation*

Patients will be enrolled in study groups in consecutive stages, according to enrollment criteria described above

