3.7. Data collection

Clinical data will be collected at certain time points of this study. The requirements to data collection and study visit schedule are given in table 1.

Table 1: Study stages and procedures

Stages / Procedures	Screening	Distribution into groups and surgery	Postoperative period (early observation: 24-48 hours)	Before discharge (ca. after 21 days)	6 months post operation ± 14 days	12 months post operation ± 30 days
	Visit No. 1	Visit No. 2	Visit No. 3	Visit No. 4	Visit No. 5	Visit No. 6
Informed consent	X					
Anamnesis morbi	X					
Physical examination, evaluation of orthopedic, somatic and neurological status	X	X	X	X	X	X
Evaluation of quality of life (GMFCS, RLAS, FIM, MACS)	X				X	X
X-ray ¹	X			X	X	X
Intraoperative control efficacy evaluation		X				

CHILDren with neuromuscular diseases – efficacy eVALuation of spinal deformity surgeRY via different pedicle screw fixation systems study
CHIVALRY study

Clinical blood analysis ²	X		X	X		X*
Biochemical blood analysis ³	X		X			X*
Spirometry*	X					X*
EchoCG*	X					X
CT ⁴	X			X		X**
MRI ⁵	X					
Documentation of serious adverse events		X	X	X	X	X

1. Spinal X-ray (from Th1 to S4), 2 standard projections.
2. RBC, hematocrit, hemoglobin, WBC, thrombocytes, ESR.
3. Total protein, creatinine, urea, bilirubin, AST/ALT, glucose.
4. Spine CT (from Th1 to S4).
5. MRI of the spine and the spinal cord.

* Performing research only for medical reasons;

** If there are signs of a bone block in the area of instrumental fixation according to the radiograph of the spine

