6. STATISTICAL ANALYSIS AND METHODS

Primary and additional quantitative efficacy and safety criteria will be summarized in shift tables and presented by means of descriptive statistics; the appropriate methods will be selected depending on the data. Missing data will be indicated as N/A and not considered in aggregate statistics. The significance of differences between data groups will be evaluated using the criteria depending on the number of observations and distribution type of parameter values within groups. Software: Statistical Package for the Social Sciences (SPSS), v. 22.0 (SPSS Inc., Chicago, IL, USA). T-criteria: 1) comparison of correction of sagittal and frontal spinal deformity components with graded FC parameters. Differences will be considered significant if two-sided $p < 0.05$.

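### The only test named in section 6 relates deformity correction to an undefined FC grade with no term for starting deformity or study group (minor; ancillary analysis)

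*Combined protocol and SAP*

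**What the plan says.** Section 6 leaves most methods to be chosen once the data are seen. The one test it names is "T-criteria: 1) comparison of correction of sagittal and frontal spinal deformity components with graded FC parameters". The threshold is given once, for all comparisons: "Differences will be considered significant if two-sided" p is below 0.05. Other between-group testing is planned but not specified: "The significance of differences between data groups will be evaluated using the criteria", with the choice resting on sample size and distribution. The section mentions no covariate, no rule for several tests and no exploratory label.

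FC is not defined anywhere. Section 1.1 uses functional class in connection with GMFCS and says that wheelchair patients ("III functional class by GMFCS - Gross Motor Function Classification System) have high risks of severe deformities in comparison with the bed-bound patients") are at greater risk, because of constant axial load. GMFCS is scheduled in Table 1 of section 3.7, in the row "Evaluation of quality of life (GMFCS, RLAS, FIM, MACS", at screening, 6 months and 12 months.

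On treatment, section 1.3 states "The type of surgical correction will depend on the group". Section 3.3 gives group 1 (growing skeleton, connector systems) N = 30 and group 2 (mature skeleton, multiple fixation points) N = 40, and describes the design: "This study is prospective, non-randomized, single-center, open and non-comparative; it involves two parallel groups of patients".

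**The concern.** The protocol's own background supplies a possible confounder. If functional class goes with starting deformity, and a larger curve leaves more degrees to correct, FC grades can differ in degrees of correction even when the relative effect of surgery is the same in every grade. A t-criterion cannot separate the two. Pooling both study groups adds a second route: the operation follows the group, so unequal FC mixes in groups 1 and 2 would carry any difference between operations into the FC comparison.

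Section 3.1 plans diagnostic and surgery-planning algorithms that take functional status into account ("Considering patient condition, deformity progression, age, physical, motor, cognitive, functional, static and dynamic status present the following"). An FC difference that really came from starting angle or group mix could be read as guidance. With no randomization, only the analysis can guard against this.

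**Working it through.** The plan states no power, effect size, SD or error-rate figure for this test, so there is nothing to reproduce. The only check available on the stated sizes is 30 + 40 = 70, which agrees with section 1.3.

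**Inputs from the documents:** N = 70 (30 and 40); two planes; two-sided 0.05 per test; a stated link between functional class and deformity severity, without a size. **Assumed, because the documents are silent:** Cobb SD, residual SD, fraction corrected, baseline gap, FC split and FC mix by group.

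**1. Starting deformity omitted.** Let correction = f × screening angle + residual, with the same f in every FC grade, so FC has no effect of its own. For two FC classes whose mean screening angles differ by a gap:
- Expected difference in correction = f × gap.
- SD of correction = √[(f × SD of Cobb)² + (residual SD)²] = √[(0.5 × 20)² + 10²] = 14.14 degrees.
- Standard error, 35 v 35 = 14.14 × √(2/35) = 3.38 degrees.
- Noncentrality = 0.5 × gap / 3.38, with 68 degrees of freedom.

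| Baseline gap (degrees) | Noncentrality | Probability of p < 0.05 |
|---|---|---|
| 0 | 0 | 5% |
| 2 | 0.30 | 6% |
| 5 | 0.74 | 11% |
| 10 | 1.48 | 31% |
| 15 | 2.22 | 59% |
| 20 | 2.96 | 83% |

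Varying f over 40% to 60%, the SD pairs over 20/10 and 25/12, and the split over 35/35 and 50/20 gives 16% to 35% at 10 degrees and 48% to 89% at 20 degrees.

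A simulation in SD units agrees. With 35 v 35 and a correlation of 0.3 to 0.7 between baseline and correction, rejection is 9.5% to 30.4% for a 0.5 SD gap and 23.4% to 82.4% for a 1 SD gap. With 20 v 20 it is 7.5% to 18.7% and 14.9% to 57.4%. With screening angle in the model it returns to about 5% throughout. That is expected, since the data were generated from a model of that form.

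If correction is expressed as a percentage of the starting angle, the expected value is f in both classes whatever the gap, and the bias disappears under this model. Section 6 does not say which measure is meant.

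**2. Group omitted.** Suppose groups 1 and 2 (30 v 40) differ by 1 SD in correction and FC has no effect. A pooled t-test rejects in about 20% of simulated trials if an FC class makes up 35% of group 1 and 65% of group 2, and in 43% to 47% if the mix is 25% v 75%. With a 0.5 SD group difference the figures are 8% to 9% and 14% to 17%. The ranges are the spread between simulation runs. With group in the model, rejection is about 5%.

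**3. Two planes.** With one test per plane and independent planes, the chance of at least one false positive is 1 − 0.95² = 9.75%. If the two test statistics correlate at 0.3 to 0.9, it is 9.5% to 7.0%.

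**The case against.** Several points on the other side are sound.

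- **The form of the test is not settled.** The wording could mean relating correction to FC, or a paired look at functional status after surgery, which section 3.1 also plans. Under a paired reading the figures above do not apply. What stands on any reading is that FC and the comparison are undefined.
- **A baseline gap in this sample is not established.** Section 1.1 contrasts wheelchair with bed-bound patients and gives no size. Section 3.6 admits only deformities that require surgery, and that selection may shrink any gap. At 2 to 5 degrees the inflation is slight.
- **A reader might infer error rates of 19% to 23% with three FC grades, or up to 49% with five, from testing every pair of grades.** Section 6 plans no all-pairs testing and no search over cut-points. It lets the method depend on the data, so an overall test is not excluded, and the number of grades is itself an assumption. The documents support only the two-plane figure.
- **A reader might infer that there is no error control at all.** A per-test two-sided 0.05 level is stated; what is missing is a rule across tests.
- **The consequence is limited.** The comparison is neither the primary nor a listed secondary endpoint, the design is non-comparative, and section 3.1 does not tie its algorithms to this p-value.

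These points lower the priority. They do not supply the missing definition or the missing baseline and group terms.

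**Conclusion.** The point holds as a minor one. The only named test uses an undefined factor and, if it compares FC grades, leaves out two variables that the protocol itself connects with functional class or with the operation. The bias from starting deformity may be negligible (about 6% false rejection at a 2-degree gap) or large (83% at 20 degrees). These figures rest on proportional correction in degrees and on the assumed SDs and split. The group-mix figures likewise rest on assumed shifts and mixes. The two planes alone take the chance of at least one false positive to at most about 10%.

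The documents do not support a claim that the study's main conclusion is at risk, or that FC grades differ at screening by any particular amount. What is at risk is the interpretation of the FC p-values.

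**What to change.** In section 6:

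1. Define FC: the scale, and the visit at which the grade is taken. State what is being compared.
2. For each plane, replace the t-criterion with a linear model of 12-month Cobb angle on screening Cobb angle, group (1 or 2) and FC as a categorical factor. Use one overall FC test per plane, and combine sparse grades by a rule set in advance. With screening angle in the model, the FC coefficients are the same apart from sign whether the outcome is the 12-month angle or degrees of correction.
3. Report adjusted means or differences with 95% CIs.
4. Label the analysis exploratory, and state that no difference is attributed to the fixation system.

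FC should be categorical, not a linear score. Section 1.1 puts class III at higher risk than bed-bound patients and says nothing about milder classes, so a mid-scale peak is plausible. With three near-equal grades, N = 70, a middle grade that differs by 8 degrees and residual SD 10 (all assumed), a linear score rejects in about 3% to 4% of simulated trials and a categorical term in 79%. A formal multiplicity adjustment over the two planes is optional once the analysis is labelled exploratory.

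The cost is wording, a few degrees of freedom and less precision in sparse grades. Cobb angles at screening and 12 months and GMFCS are already scheduled, so no visit, test or patient is added.

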7. REPORT AND DATA PUBLICATIONS

CHILDren with neuromuscular diseases – efficacy eVALuation of spinal deformity surgeRY via different pedicle screw fixation systems study
CHIVALRY study

Intermediate reports are planned to be provided to Medtronic and the LEC throughout the study. Upon completion of the study all study data will be analyzed and a final study report drawn to be provided to Medtronic and the LEC. Study results are also intended to be published and presented at professional events having the materials preliminarily approved by Medtronic. The expected time of publication of final results – 2020-2021.

The study will be registered at the international resource for clinical trials: www.clinicaltrials.gov.
